6.2. Exclusion Criteria

Eligible patients must not meet any of the following exclusion criteria:

- 1. Histology other than astrocytoma grade IV (GBM or gliosarcoma).
- 2. Tumor foci detected below the tentorium or beyond the cranial vault.
- 3. Glioblastoma or gliosarcoma disease with leptomeningeal spread.
- 4. Patients with a history of any other cancer, unless in complete remission, and off all therapy for that disease for a minimum of 5 years (except history of basal or squamous cell skin cancers that are completely excised/cured at time of enrollment).
- 5. Patients with serum aspartate aminotransferase (AST), alanine aminotransferase (ALT) > 2.5 X_the upper limit of normal (ULN) and bilirubin >1.5 ULN, (unless there is a medical justification for the elevation of bilirubin and ALT, AST).
- 6. Moderate to severe hepatic impairment, i.e., Child-Pugh Class B/C.

- 7. Positive results from HIV serology testing, if any available.
- 8. Supine systolic blood pressure < 100 mmHg or supine diastolic blood pressure < 50 mmHg at screening and baseline, or documented medical history of orthostatic hypotension.
- 9. Renal insufficiency (estimated creatinine clearance < 50 mL/min) or serum creatinine >1.5 X ULN at screening.
- 10. Females who are pregnant or lactating or plan to become pregnant during the course of this study.
- 11. Substance or alcohol abuse or dependence, within 12 months prior to screening.
- 12. Prior chemotherapy for recurrent GBM with nitrosourea compounds including Gliadel® (carmustine) wafers or bevacizumab.
- 13. Prior focal radiotherapy (stereotactic radiotherapy or Gamma Knife) within 3 months of screening.
- 14. Planned treatment, or treatment with any investigational drug within 4 weeks prior to screening.
- 15. Severe, active co-morbidity, including: Cardiac disease congestive heart failure class III/IV NYHA; unstable angina or new onset angina (began within the last 3 months) or acute or chronic myocardial infarction within the past 6 months; cardiac ventricular arrhythmias requiring anti-arrhythmic therapy; cerebrovascular accident within 6 months prior to enrollment; acute bacterial or fungal infection requiring intravenous antibiotics at the time of screening; chronic hepatitis B or C infection; chronic obstructive pulmonary disease exacerbation or other respiratory illness requiring hospitalization or precluding study therapy at the time of screening; hematological and bone marrow diseases. Severe malabsorption (defined as > 15% unintentional loss of body weight in the last 6 months prior to study enrollment), Major medical illnesses or psychiatric impairments that, in the investigator's opinion, will prevent administration or completion of protocol therapy.
- 16. Patients who are currently taking Coumadin or Coumadin derivatives other than to maintain patency of venous access lines.
- 17. Requiring renal dialysis
- 18. Receiving hematopoietic growth factors
- 19. Have significant baseline neuropathies (> grade 2 based upon CTCAE v 4.03)
- 20. Had prior exposure to gene vector delivery products within 6 months
- 21. Any condition that prevents compliance with the protocol or adherence to therapy.
- 22. Active, uncontrolled bacterial, viral, or fungal infections, requiring systemic therapy.

- 23. Treated with antibiotics for infection within one week prior to study entry.
- 24. Fever (> 38.1°C)
- 25. Have diastolic blood pressure of > 90 mm Hg resting at baseline despite medication. (Acceptable if on hypertensive medication and diastolic blood pressure is < 90 mm Hg.).
- 26. Serious nonmalignant disease (e.g., hydronephrosis, liver failure, or other conditions) that could compromise protocol objectives in the opinion of the Investigator and/or the Sponsor.
- 27. Enrollment in a concomitant clinical study
- 28. Have a history of hypersensitivity reaction (such as urticaria, allergic reaction including anaphylaxis, toxic epidermal necrolysis, and Stevens-Johnson syndrome) to any of the components of Temozolomide
- 29. Have a history of hypersensitivity to dacarbazine (DTIC)

6.2.1. Concomitant Medications:

Allowed concomitant medications

Concomitant medications permitted during all study periods include:

- Anti-epileptics
- Oral corticosteroids, provided that the dose is stable for at least 5 days prior to each contrast-enhanced brain MRI performed to assess tumor progression. Any change in the dose of corticosteroids must be recorded in the Case Report Form (CRF).
- Other concomitant medications: therapies considered necessary for the well-being of the patient may be given at the discretion of the treating physicians for both prophylaxis and treatment (e.g., anti-emetic).

All concomitant medications must be recorded in the CRF.

Prohibited concomitant medications

Concomitant medications prohibited during all study periods include:

- Concurrent treatment with bevacizumab or nitrosourea, including Gliadel® wafers.
- Cytotoxic chemotherapy other than TMZ.
- Any investigational drug other than the study drugs.

6.2.2. Concomitant Procedures:

If whilst on protocol, a patient needs surgery for tumor progression or brain surgery for other causes e.g. hydrocephalus, bleeding, the patient can be continued on the study at the discretion of the investigator.

7. STUDY DRUGS:

7.1. Temozolomide (Temodar®) (NDC 0085-1366)

a. DESCRIPTION

4-Methyl-5-oxo-2,3,4,6,8-pentazabicyclo[4.3.0]nona-2,7,9-triene-9-carboxamide (Temozolomide) is a white-to-off-white crystalline powder with a molecular weight of 194.1508

Mechanism of Action: Temozolomide is an imidazotetrazine derivative Temozolomide is not directly active but undergoes rapid nonenzymatic conversion at physiologic pH to the reactive compound 5-(3-methyltriazen-1-yl)-imidazole-4-carboxamide (MTIC). The cytotoxicity of MTIC is thought to be primarily due to alkylation of DNA. Alkylation (methylation) occurs mainly at the O^6 and N^7 positions of guanine.

b. TOXICOLOGY

Human Toxicology:

In patients with newly diagnosed Glioblastoma Multiforme, during the concomitant phase (temozolomide+radiotherapy), adverse reactions including thrombocytopenia, nausea, vomiting, anorexia, and constipation were more frequent in the temozolomide+RT arm. The incidence of other adverse reactions was comparable in the two arms. The most common adverse reactions across the cumulative temozolomide experience were alopecia, nausea, vomiting, anorexia, headache, and constipation. Forty-nine percent (49%) of patients treated with temozolomide reported one or more severe or life-threatening reactions, most commonly fatigue (13%), convulsions (6%), headache (5%), and thrombocytopenia (5%). Overall, the pattern of reactions during the maintenance phase was consistent with the known safety profile of temozolomide.

Myelosuppression (neutropenia and thrombocytopenia), which is a known dose-limiting toxicity for most cytotoxic agents, including temozolomide, was observed. When laboratory abnormalities and adverse reactions were combined, Grade 3 or Grade 4 neutrophil abnormalities including neutropenic reactions were observed in 8% of the patients, and Grade 3 or Grade 4 platelet abnormalities, including thrombocytopenic reactions, were observed in 14% of the patients treated with temozolomide.

In patients with refractory anaplastic astrocytoma, the most frequently occurring adverse reactions were nausea, vomiting, headache, and fatigue. The adverse reactions were usually NCI Common Toxicity Criteria (CTC) Grade 1 or 2 (mild to moderate in severity) and were self-limiting, with nausea and vomiting readily controlled with antiemetics. The incidence of severe nausea and vomiting (CTC Grade 3 or 4) was 10% and 6%, respectively. Myelosuppression (thrombocytopenia and neutropenia) was the dose limiting adverse reaction. It usually occurred within the first few cycles of therapy and was not cumulative. Myelosuppression occurred late in the treatment cycle and returned to normal, on average, within 14 days of nadir counts. The median nadirs occurred at 26 days for platelets (range: 21-40 days) and 28 days for neutrophils (range: 1-44 days). Only 14% (22/158) of patients had a neutrophil nadir and 20% (32/158) of patients had a platelet nadir, which may have delayed the start of the next cycle. Less than 10%

of patients required hospitalization, blood transfusion, or discontinuation of therapy due to myelosuppression.

In clinical trial experience with 110 to 111 women and 169 to 174 men (depending on measurements), there were higher rates of Grade 4 neutropenia (ANC <500 cells/ μ L) and thrombocytopenia (<20,000 cells/ μ L) in women than men in the first cycle of therapy (12% vs. 5% and 9% vs. 3%, respectively).

In the entire safety database for which hematologic data exist (N=932), 7% (4/61) and 9.5% (6/63) of patients over age 70 experienced Grade 4 neutropenia or thrombocytopenia in the first cycle, respectively. For patients less than or equal to age 70, 7% (62/871) and 5.5% (48/879) experienced Grade 4 neutropenia or thrombocytopenia in the first cycle, respectively. Pancytopenia, leukopenia, and anemia have also been reported.

Contraindication:

Temozolomide is contraindicated in patients who have a history of hypersensitivity reaction (such as urticaria, allergic reaction including anaphylaxis, toxic epidermal necrolysis, and Stevens-Johnson syndrome) to any of its components. TEMODAR is also contraindicated in patients who have a history of hypersensitivity to DTIC, since both drugs are metabolized to 5-(3-methyltriazen-1-yl)-imidazole-4-carboxamide (MTIC).

Pregnancy and Lactation: Temozolomide can cause fetal harm when administered to a pregnant woman. Male and female patients who take temozolomide should use effective birth control. Female patients and female partners of male patients should avoid becoming pregnant while taking temozolomide. Administration of temozolomide to rats and rabbits during organogenesis at 0.38 and 0.75 times the maximum recommended human dose (75 and 150 mg/m2), respectively, caused numerous fetal malformations of the external organs, soft tissues, and skeleton in both species. There is no data on temozolomide administration during human pregnancy, and it is not currently known if metabolites are excreted in human milk. However, many drugs are excreted in human milk, and there is a potential for adverse effects in nursing infants. Therefore, the use of temozolomide should be avoided in pregnant or nursing women because of the potential hazard to the fetus or infant.

c. PHARMACOLOGY

Kinetics: Absorption: Temozolomide is rapidly and completely absorbed after oral administration with a peak plasma concentration (Cmax) achieved in a median Tmax of 1 hour. Food reduces the rate and extent of temozolomide absorption. Mean peak plasma concentration and AUC decreased by 32% and 9%, respectively, and median Tmax increased by 2-fold (from 1-2.25 hours) when temozolomide was administered after a modified high-fat breakfast. A pharmacokinetic study comparing oral and intravenous temozolomide in 19 patients with primary CNS malignancies showed that 150 mg/m² TEMODAR for injection administered over 90 minutes is bioequivalent to 150 mg/m² TEMODAR oral capsules with respect to both Cmax and AUC of temozolomide and MTIC. Following a single 90-minute intravenous infusion of 150 mg/m², the geometric mean Cmax values for temozolomide and MTIC were 7.3 mcg/mL and 276 ng/mL, respectively. Following a single oral dose of 150 mg/m², the geometric mean

Cmax values for temozolomide and MTIC were 7.5 mcg/mL and 282 ng/mL, respectively. Following a single 90-minute intravenous infusion of 150 mg/m², the geometric mean AUC values for temozolomide and MTIC were 24.6 mcg·hr/mL and 891 ng·hr/mL, respectively. Following a single oral dose of 150 mg/m², the geometric mean AUC values for temozolomide and MTIC were 23.4 mcg·hr/mL and 864 ng·hr/mL, respectively.

Distribution: Temozolomide has a mean apparent volume of distribution of 0.4 L/kg (%CV=13%). It is weakly bound to human plasma proteins; the mean percent bound of drug-related total radioactivity is 15%. Metabolism and Elimination: Temozolomide is spontaneously hydrolyzed at physiologic pH to the active species, MTIC and to temozolomide acid metabolite. MTIC is further hydrolyzed to 5-amino-imidazole-4-carboxamide (AIC), which is known to be an intermediate in purine and nucleic acid biosynthesis, and to methylhydrazine, which is believed to be the active alkylating species. Cytochrome P450 enzymes play only a minor role in the metabolism of temozolomide and MTIC. Relative to the AUC of temozolomide, the exposure to MTIC and AIC is 2.4% and 23%, respectively.

Excretion: About 38% of the administered temozolomide total radioactive dose is recovered over 7 days: 37.7% in urine and 0.8% in feces. The majority of the recovery of radioactivity in urine is unchanged temozolomide (5.6%), AIC (12%), temozolomide acid metabolite (2.3%), and unidentified polar metabolite(s) (17%). Overall clearance of temozolomide is about 5.5 L/hr/m². Temozolomide is rapidly eliminated, with a mean elimination half-life of 1.8 hours, and exhibits linear kinetics over the therapeutic dosing range of 75 to 250 mg/m²/day.

Formulation: 100mg capsules of temozolomide are supplied as a white capsule with a pink cap. The capsules contain temozolomide and inactive ingredients lactose anhydrous, colloidal silicon dioxide, sodium starch glycolate, tartaric acid, and stearic acid in the form of a white powder. The body of the capsules are made of gelatin and are opaque white. The cap is also made of gelatin, and the colors vary based on the dosage strength.

Storage and Stability: Store temozolomide Capsules at 25°C (77°F); excursions permitted to 15°-30°C (59°-86°F).

Administration: Oral

Handling Precautions: Care should be exercised in the handling and preparation of TEMODAR. Vials and capsules should not be opened. If vials or capsules are accidentally opened or damaged, rigorous precautions should be taken with the contents to avoid inhalation or contact with the skin or mucous membranes. The use of gloves and safety glasses is recommended to avoid exposure in case of breakage of the vial or capsules. Procedures for proper handling and disposal of anticancer drugs should be considered. (1)

d. SUPPLIER

The doses are given as mg of wtp53 plasmid DNA. The complex is prepared at a specific ratio of 1 ug of DNA to a specific amount of TfRscFv and a specific amount of liposome. Therefore, as the amount of DNA increases, the amount of TfRscFv and liposome in the complex increases proportionally. The complex will then be mixed with 5% Dextrose for infusion. The final volume of the complex/5% Dextrose per infusion will be ~200 ml and will be infused intravenously over 90-120 minutes.

The complex diluted in 5% Dextrose (at ratios of 1:2 to 1:5) is stable for at least eight hours at 20°C once prepared. Infusion of the complex should be initiated within one hour of preparation and the infusion completed within eight hours of dilution of study agent in dextrose.

The investigator will be responsible for dispensing and accounting of all components of the complex provided by the sponsor. Records of document control numbers and dates received will be kept on a Drug Inventory Form provided by the sponsor. Under no Protocol Number: SGT53-02-2 Amendment 6 July 5, 2016 circumstances will the investigator supply

circumstances will the investigator supply study drug to other investigators, allow study drug to be used other than directed by this protocol, or destroy or dispose of study drug in any other manner without prior authorization from the sponsor.

Any residual clinical trial materials must be returned to the clinical site's investigational drug pharmacy for disposition. All unopened or partially used vials of the SGT-53 components will be returned to SynerGene Therapeutics, Inc. at the end of the study.

Reconstitution:

With sterile WFI as directed by Sponsor supplied SOP

Administration: Intravenous.

Handling Precautions:

None to date.

d. SUPPLIER

SGT-53 is not commercially available. It is provided free of charge by the Sponsor

SynerGene Therapeutics, Inc [name]

[contact]

Email: [contact]

8. STUDY ENDPOINTS:

8.1. Safety Endpoint Definitions

Patients will be evaluated and adverse events (AEs) assessed according to the Study Calendar (Section 18.1) using Common Toxicity Criteria 4.0 (CTC 4.03, 2010). For definition of DLT see Section 9.7.

8.2. Efficacy Endpoints

To evaluate the PFS, 6 month PFS, OS in patients treated with SGT-53 in combination with Temozolomide. These parameters will be evaluated using RANO Response Criteria (Response Assessment in Neuro-Oncology). All patients who have measureable disease according to RANO, received at least one dose of SGT-53, and have had disease reevaluated will be included in the analyses of secondary endpoints.

Optional surgical resection for tumor analysis:

DNA PCR will be employed to determine the presence of the nanoparticle delivered exogenous wtp53 gene in the tumor sample obtained during surgical resection. A maximum of 6 patients will be have this optional testing. Detection of exogenous wtp53 in the tumors from at least 3 patients will be considered a positive outcome. If the presence of the exogenous wtp53 is detected in at least 3 of the first 4 tumors assessed, the option for surgical resection for tumor analysis will no longer be offered.

9. TREATMENT PLAN:

Cycles 1-3 (1 Cycle is 28 days)

- Day 1: SGT infusion
- Day 4: SGT infusion
- Day 8: SGT infusion
- Days 9-13: TMZ (150mg/m2 increasing to 200mg/m2 as tolerated, provided the patient meets the criteria for non-hematological toxicity, ANC and platelet counts)
- Day 11: SGT infusion
- Day 15: SGT infusion
- Day 18: SGT infusion
- Days 19-28: No treatment

In those patients who had a surgical resection, the 1st cycle of SGT-53 and TMZ will start 14-21 days post operatively and having recovered from the effects of surgery.

Cycles 4-6: Patients who are responding to treatment (at least stable disease by RANO) may receive three additional cycles of SGT-53/Temozolomide therapy at investigator's discretion. Alternatively, they may continue on Temozolomide alone at investigator's discretion.

Optional surgical resection for tumor analysis (Maximum of 6 Patients):

[figure not shown]
- SGT infusion on days -3 and -1
- Surgery on Day 0
- 14- 21 days post operatively and having recovered from the effects of surgery, the patients will then start cyclical TMZ with SGT-53 as described above: SGT-53 will be administered every 3rd or 4th day in a 28 day cycle (total of 6 infusions)] starting on Day 1 (cycle 1), Day 29 (cycle2) and Day 57 (cycle 3). The day of the first post-surgical infusion of SGT-53 will be Day 1 (cycle 1). Temozolomide will be administered by mouth daily on days 9-13 of each cycle at 150mg/m2 (cycle 1), and 200mg/m2 as tolerated for cycle 2 and beyond provided the patient meets the criteria for non-hematological toxicity, ANC and platelet counts (see 9.7.2).
- Patients who are responding to treatment (at least stable disease by RANO) may receive three additional cycle of SGT-53/Temozolomide therapy at investigator's discretion. Alternatively, they may continue on Temozolomide alone at investigator's discretion.

9.1. Dosing Plan:

Administration of SGT-53 and Temozolomide therapy

Agent	Dose	Route
Temozolomide	150 mg/m ² (starting dose)	Oral
SGT-53	3.6mg DNA per infusion	IV over 90-120 minutes

[figure not shown]

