Surgical resection for tumor analysis before the commencement of SGT-53/Temozolomide treatment is an optional procedure. For these patients, SGT-53 will be administered twice during the week prior to surgical resection of the tumor. 14-21 days post-surgical resection, patients will receive SGT-53 and Temozolomide in 28 day cycles. These patients who respond to treatment (at least stable disease by RANO) may receive three additional cycle of SGT-53/Temozolomide therapy at investigator's discretion. The primary objective of this surgical resection is to assess nanoparticle tumor delivery by analysis of the presence of exogenous wt p53 in the tumor.

All patients enrolled in the study will be evaluated for PFS, PFS-6 and OS.

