4.6.3.1 Primary Endpoints

PFS-6 using the RANO criteria (see Section 18.2) will be used as primary endpoints.

4.6.3.2.Secondary Endpoints

- Safety of the combination of SGT-53 and Temozolomide.
- PFS, OS
- Anti-tumor activity of the combination of SGT-53 and Temozolomide based upon the RANO criteria.
- The induction of apoptosis by SGT-53 in the tumor (optional procedure).
- Nanoparticle delivery (optional procedure)

4.6.4. Statistical hypothesis and sample size:

A total of 26 patients will be enrolled. A maximum of 6 patients will be enrolled to participate in the optional surgical resection for tumor analysis.

Patients who have received at least one dose of study drug will be considered evaluable for safety and toxicity endpoints. Patients who require a dose interruption or reduction during the initial cycle will remain evaluable for toxicities if the reduction or interruption is due to a DLT. Patients who do not complete one cycle of treatment but do not have a DLT may be replaced as described in more detail in Section 9.6.

The primary endpoint for the trial is PFS6. Progression-free survival will be defined as the time from study enrollment until the time of first occurrence of disease progression, relapse, or death due to disease.

The analysis of the biological correlate data in patients with surgical resection for tumor analysis has the overall goal of providing an increased understanding of the ability of SGT-53 to cross the Blood-brain Barrier and be delivered into tumor cells in the brain. As such, the objective of the tumor analysis is qualitative rather than quantitative. It should be noted that in the Phase I dose escalation trial of SGT-53, the presence of the exogenous wtp53 delivered by SGT-53 was found to be present in the tumors in a DNA dose dependent manner. Moreover, even the lowest dose of SGT-53 (0.6mg DNA/infusion) was not only found to be present in the tumors of the patients, but to have some anti-tumor effect. A DNA dose 6-fold higher (3.6mg DNA/infusion) is being used in this trial.

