Reverse transcription PCR to determine transgene expression is not applicable for these studies because it would not be able to unequivocally establish that the p53 protein detected was from the exogenous transgene. In contrast, since we have designed primers that included part of the plasmid vector backbone, only the exogenous DNA is amplified. This DNA PCR approach was used to detect the presence of the transgene in the tumors in the Phase I trial (See Figures 16 and 17 in Section 4.4.1.1) and will be used for these studies. The presence of at least 30 copies of exogenous p53 in the tumors sample will be considered positive evidence of drug penetration.

All of the patients in the trial will receive the same dosing of the combination of SGT-53 and TMZ (6 doses of SGT-53 and 5 doses of TMZ every 4 weeks for three 4 week cycles) and thus patients with or without surgical resection for tumor analysis will be used for the Simon two stage calculation. Even for the patients who undergo the optional surgical resection for tumor analysis PFS6 is the primary endpoint. No TMZ will be administered during the time these patients receive the two doses of SGT-53 prior to the resection. Exogenous p53 expression is transient. The patients who receive surgery will not begin treatment for 2-3 weeks post-surgery. Previous studies have demonstrated that there is no indication of the exogenous wtp53, even by DNA PCR, after this length of time. Thus, there will be no additional residual DNA present from the two pre-surgery doses of SGT-53 by the time the combination therapy being evaluated is initiated.

According to the Simon Minimax design, our study, with its sample size of n = 26, has a 10% probability of rejecting (a) the hypothesis of a PFS6 15% (P0) (the historical PFS6 rate) and a 70% probability of accepting (1-b) the hypothesis of a PFS-6 of 30% (P1). If two, or fewer of the first 18 patients were progression free at 6 months, PFS-6 would be considered <15% and the study terminated. Otherwise, the study would be completed, the accrual target being 26 patients. If six or fewer of the 26 patients were progression-free at 6 months, then no further investigation of the treatment regimen would be considered warranted. PFS6 and secondary endpoints progression free survival and overall survival will be evaluated using the Kaplan-Meier product-limit survival curve methodology.

4.6.5. Study Objectives:

Primary:

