10.4. Efficacy Assessments

10.4.1. Progression-Free Survival

The percentage of patients who are alive and progression-free clinically and radiologically 6 and 12 months after starting treatment will be evaluated using the Kaplan-Meier method. Progression is defined by any of the following using the RANO criteria:

- a) >25% increase in sum of the products of perpendicular diameters of enhancing lesions compared with the smallest tumor measurement obtained either at baseline (if no decrease) or best response, on stable or increasing doses of corticosteroids*.
- b) Significant increase in T2/FLAIR non-enhancing lesion on stable or increasing doses of corticosteroids compared with baseline scan or best response after initiation of therapy *not caused by co-morbid events (e.g. radiation therapy, demyelination, ischemic injury, infection, seizures, postoperative changes, or other treatment effects)
- c) Any new lesion

- d) Clear clinical deterioration not attributable to other causes apart from the tumor (e.g. seizures, medication adverse effects, complications of therapy, cerebrovascular events, infection, and so on) or changes in corticosteroid dose
- e) Failure to return for evaluation as a result of death or deteriorating condition
- f) Clear progression of non-measurable disease

Note: All measurable and non-measurable lesions must be assessed using the same techniques as at baseline.

*Stable doses of corticosteroids include patients not on corticosteroids.

10.4.2. Tumor response rate:

The percentage of patients with a complete or partial response 6 and 12 months after starting treatment will be evaluated using the RANO criteria:

Complete response (CR). Requires all of the following

- a) complete disappearance of all enhancing measurable and non-measurable disease sustained for at least 4 weeks
- b) no new lesions
- c) stable or improved non-enhancing (T2/FLAIR) lesions
- d) patients must be off corticosteroids (or on physiologic replacement doses only)
- e) stable or improved clinically

Note: Patients with non-measurable disease only cannot have a complete response; the best response possible is stable disease.

Partial response (PR). Requires all of the following:

- a) >50% decrease compared with baseline in the sum of products of perpendicular diameters of all measurable enhancing lesions sustained for at least 4 weeks
- b) No progression of non-measurable disease
- c) No new lesions

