10.4.4. Overall survival

Overall survival is defined as the time from treatment initiation to death or to time last seen alive. The overall survival rate will be estimated by the proportion of patients who are alive at EOS and 12 months after starting treatment using the Kaplan-Meier method.

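### Section 8.2 limits the secondary-endpoint analyses to patients whose disease was re-evaluated, a term it does not define; applied to PFS and OS, this leaves out the earliest failures and contradicts other sections.

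*Combined protocol and SAP*

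**What the plan says.** Section 8.2 opens by naming PFS, 6-month PFS and OS, to be evaluated by the RANO criteria. It then sets out who enters the secondary analyses: patients with measurable disease who "received at least one dose of SGT-53, and have had disease reevaluated will be included in the analyses of secondary endpoints". The documents give no other analysis set for secondary endpoints. They do not say what counts as re-evaluation (a scan or a clinical visit), from when, or whether death or failure to return satisfies it.

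PFS and OS are listed as secondary in the synopsis and in Section 4.6.3.2. Section 4.6.4 adds that "secondary endpoints progression free survival and overall survival will be evaluated using the Kaplan-Meier product-limit survival curve methodology".

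Other sections describe a different population or a different handling of early failures:

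- Section 4.5.1: "All patients enrolled in the study will be evaluated for PFS, PFS-6 and OS".
- Section 10.4.1, items d and e, count as progression "Clear clinical deterioration not attributable to other causes apart from the tumor" and "Failure to return for evaluation as a result of death or deteriorating condition".
- Section 10.4.4: "Overall survival is defined as the time from treatment initiation to death or to time last seen alive". No disease reassessment is needed.
- Section 4.6.4 defines the PFS event as "first occurrence of disease progression, relapse, or death due to disease", which is narrower on deaths than item e of Section 10.4.1.
- Section 4.6.4, for safety: "Patients who have received at least one dose of study drug will be considered evaluable for safety and toxicity endpoints".

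**The concern.** Re-evaluation happens after treatment starts, so whether a patient satisfies the condition depends partly on outcome. Those who fail it are the patients who die, or become too ill to be assessed, soonest. Section 10.4.1 treats such a patient as an event, while Section 8.2 places the same patient outside the analysis.

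The direction is clear in two cases. Removing early deaths raises the OS curve, and removing early deaths or progressions raises the PFS curve. A patient who only deteriorates and is never re-evaluated also leaves the OS set, but no direction is claimed for OS from that loss.

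The trial has one arm, so there is no control group in which the same selection would show. The reported curves, medians and 12-month rates are what readers would set against historical figures. A secondary PFS curve read at 6 months could also disagree with the primary PFS6 result from the same trial, because the denominators differ. Two incompatible populations in an open-label study also leave the choice open until the data have been seen.

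**Working it through.** **The primary rule.** Section 4.6.4 gives a Simon minimax design: stop if 2 or fewer of 18 are progression-free at 6 months, and declare the regimen not worth pursuing if 6 or fewer of 26 are, for 15% against 30% at a nominal 10% error and 70% power. Exact binomial enumeration reproduces it: error 0.083, power 0.701, probability of early stopping 0.480 at a true rate of 15%. The denominators are fixed at 18 and 26, and the Section 8.2 sentence concerns secondary endpoints only, so it does not change this rule.

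**Inputs for the illustration.**
- Median survival of about 6 months (Section 4.5.1); historical PFS6 of 15% and n = 26 (Section 4.6.4).
- First scheduled on-treatment MRI at Cycle 2, D23–D28 (Section 18.1), that is study days 51–56.
- First clinic visit after Day 1 on Day 4, with vital signs, performance status and medical history, which includes adverse events (Section 18.1.1).
- Assumptions: exponential curves; 1 month = 30.44 days, so 56 days = 1.840 months.

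**Formulas.** OS: S(t) = 2^(−t/6), so S(12) = 25.0%. PFS: hazard −ln(0.15)/6 = 0.316 per month, median ln 2/0.316 = 2.19 months. If a fraction f of patients, all early failures, is dropped, then after the early window S*(t) = S(t)/(1−f). The OS median becomes 6 × [1 − log2(1−f)] and the PFS median ln[2/(1−f)]/0.316.

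**Fraction dropped.**
- A clinical visit counts, first one on Day 4: 3 to 4 days of follow-up is 0.099 to 0.131 months, so f = 1 − 2^(−0.099/6) = 0.011 to 1 − 2^(−0.131/6) = 0.015.
- One or two patients: 1/26 = 0.038 or 2/26 = 0.077.
- Only the scheduled MRI counts and every earlier death is lost: f = 1 − 2^(−1.840/6) = 0.1915, or 0.1915 × 26 = 5.0 patients.

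| Patients dropped (of 26) | Median OS, months | 12-month OS | Median PFS, months | 6-month PFS |
|---|---|---|---|---|
| 0 | 6.0 | 25.0% | 2.2 | 15.0% |
| 0.3–0.4 (Day 4 visit counts) | 6.1 | 25.3–25.4% | 2.2 | 15.2% |
| 1 | 6.3 | 26.0% | 2.3 | 15.6% |
| 2 | 6.7 | 27.1% | 2.5 | 16.3% |
| 5.0 (all deaths by day 56) | 7.8 | 30.9% | 2.9 | 18.6% |

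For example, 0.25/(1 − 1/26) = 0.260, 0.25/0.8085 = 0.309 and 0.15/0.8085 = 0.186.

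**Scale.** The standard error of 12-month OS at n = 26 is √(0.25 × 0.75/26) = 0.085. One lost death shifts the estimate by 1.0 point, about an eighth of that.

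**Sensitivity.** Eligible patients may do better than the general prognosis. With an assumed median of 9 months, deaths by day 56 are 1 − 2^(−1.840/9) = 0.132 (3.4 of 26). Dropping all of them moves 12-month OS from 39.7% to 0.397/0.868 = 45.7%.

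**The case against.** The strongest reply is that the exclusion is inferred. Section 8.2 says that patients meeting three conditions will be included; it does not say *only* those patients. Section 4.5.1 covers all enrolled patients, and the endpoint definitions in Sections 10.4.1 and 10.4.4 treat early failures as events. The sentence may be response-evaluability wording placed too broadly. This stands in part: the sponsor may never have meant to drop anyone. But the sentence follows directly on PFS, 6-month PFS and OS, covers all secondary endpoints as written, and has no rival as an analysis-set definition. The sections that point the other way contradict it; they do not override it.

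The second reply is that few patients would be lost. Patients are seen at least weekly (Section 10.2.3), suspected progression can bring a scan forward (Sections 10.2.1 and 10.2.2), and imaging is called for at discontinuation (Sections 9.4 and 10.2.4), though Section 9.4 asks for it only where possible and reasonable. If a clinical visit counts, the effect is negligible. This stands as to size. The text does not say which of these counts.

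A reader might infer that every PFS event before the first scheduled MRI would be lost. Under the same model that is 1 − 0.15^(1.840/6) = 44%, about 11 of 26, which would lift 6-month PFS to 26.8% and the median to 4.0 months. The documents do not support this. A living patient who progresses before day 56 still has the scheduled scan on days 51–56, is thereby re-evaluated, and stays in. Only patients who die or cannot be assessed are at risk of being dropped.

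**Conclusion.** The plan is wrong as written, with minor to moderate severity. Section 8.2, applied as the analysis set, removes from PFS and OS treated patients who die or deteriorate before an undefined re-evaluation, and it is incompatible with Sections 4.5.1, 10.4.1 and 10.4.4. That inconsistency is certain. The upward bias follows if the sentence is applied.

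The number lost is not known and is probably small: negligible if a clinical visit counts, and about 1 point of 12-month OS for each early death lost. The ceiling of 30.9% for 12-month OS and 7.8 months for the median, with 18.6% for 6-month PFS at the same 19% loss, requires that only the scheduled MRI counts and that every earlier death is dropped. The provisions for earlier scans make that unlikely. All these figures rest on exponential survival, and the OS figures also on the quoted 6-month median.

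A reader might also infer that the go/no-go decision is inflated. It is not: the Simon rule has its own fixed denominators, and no decision rule uses secondary PFS or OS.

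**What to change.** For PFS and OS, replace the Section 8.2 sentence, including its measurable-disease condition (already an entry criterion, Section 6.1 item 4), with all patients who received at least one dose of study drug. Section 4.6.4 already uses that set for safety. In addition:

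- Before any re-evaluation, count deaths, and non-return through death or deterioration, as PFS events. Count all deaths as OS events.
- State one time origin. Section 4.6.4 counts PFS from enrollment, while Sections 10.4.1, 10.4.3 and 10.4.4 count from the start of treatment. Say how it applies to optional-surgery patients dosed on days −3 and −1, who stay in the set even if they never start Cycle 1.
- Reconcile Section 4.5.1 with Section 8.2, and list any patient enrolled but never treated.
- Reconcile the restriction to disease-related death in Section 4.6.4 with item e of Section 10.4.1.
- Keep a re-evaluable set for RANO response only. Define which scans or clinical assessments count and from when, and show the all-treated response rate beside it.

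The cost is a formal amendment of wording under Section 15.4, with no new data or visits. The PFS and OS estimates may come out slightly less favourable.
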